10.4.10 Bayley-III® score

Neurodevelopmental tests validated for age and language will be done after 1 year for subjects who qualify to enter the long-term follow-up study in countries where a validated translation of the Bayley Scales of Infant and Toddler Development®, Third Edition (Bayley-III®) score is available.

Listing of Bayley-III score will be provided for the SS.

10.4.11 Withdrawal and rebound phenomena

Withdrawal and rebound phenomena will be assessed by observing any AEs experienced by subjects following the cessation of BRV administration. These AEs will be reported by the Investigators, and any AEs relating to BRV withdrawal will be used for the analysis of withdrawal and rebound phenomena. Withdrawal and rebound phenomena, if any, will be captured from data collected at the end of BRV exposure for subjects in Confirmatory Cohorts.

The following summaries will be provided for the SS: incidence of TEAEs with onset during the Down-Titration Period, incidence of TEAEs with onset during the Down-Titration Period and leading to permanent discontinuation of study medication.

A listing of AEs with onset during the Down-Titration Period will be provided for the SS.

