11.3.8 Withdrawal and rebound phenomena

Withdrawal and rebound phenomena will be assessed by observing any AEs experienced by subjects following the cessation of BRV administration. These AEs will be reported by the Investigators, and any AEs relating to BRV withdrawal will be used for the analysis of withdrawal and rebound phenomena. Withdrawal and rebound phenomena, if any, will be captured from data collected at the end of BRV exposure for subjects in both the Exploratory and Confirmatory Cohorts.

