3.2.2.1.4 Safety Follow-Up Period

Subjects will proceed to the Safety Follow-Up Period if they do not require further BRV administration. The start of the Safety Follow-up Period will be defined as after the end of the last BRV administration. The end of the Safety Follow-up Period will be defined as last contact to the subject, which will be the Follow-Up visit. This visit will occur 30 ± 3 days after the final administration of BRV.

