3.2.2.2.5 Down Titration Period

Down-Titration Period will start after the Evaluation Period or after the BRV Extension Period, can last up to 1 week. The end of the Down-Titration period is defined as day and time of last BRV administration.

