4.5 Multiple comparisons/multiplicity

Not applicable for this study. The study is not statistically powered, and all analyses are of descriptive nature. No statistical tests will be performed.

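### The withdrawal and rebound outputs in SAP 10.4.11 close at the last BRV dose and leave out the Exploratory Cohort, so post-cessation AEs are reported only in general tables, without that label

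*SAP*

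**What the plan says.** Withdrawal and rebound is one of the other safety variables in Protocol 4.3.2 and SAP 2.2.3.2, both under headings that name the Exploratory and Confirmatory Cohorts. Protocol 11.3.8 says it is assessed by "observing any AEs experienced by subjects following the cessation of BRV administration" and that the data come from both cohorts. SAP 10.4.11 states the same target, "any AEs experienced by subjects following the cessation of BRV administration", but restricts capture to the Confirmatory Cohorts.

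The outputs that SAP 10.4.11 then specifies are the "incidence of TEAEs with onset during the Down-Titration Period", the same summary limited to events leading to permanent discontinuation, and a listing: "A listing of AEs with onset during the Down-Titration Period will be provided for the SS".

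SAP 3.2.2.2.5 fixes the window. It opens as follows: "Down-Titration Period will start after the Evaluation Period or after the BRV Extension Period, can last up to 1 week". It closes as follows: "The end of the Down-Titration period is defined as day and time of last BRV administration". The first footnote to Protocol Table 5–3 limits down-titration to the Confirmatory Cohorts. For the Exploratory Cohort, SAP 3.2.2.1.4 says: "The start of the Safety Follow-up Period will be defined as after the end of the last BRV administration".

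**The concern.** The stated target is what happens after BRV stops; the outputs count what happens before it stops. Applied literally, the period definitions leave no place in the dedicated outputs for an event that begins after the last dose. The Exploratory Cohort drops out for a second reason: it has no down-titration.

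This is the first use of BRV in neonates, and withdrawal and rebound is a named safety variable. A nearly empty table under that title invites a conclusion that it could not have contradicted. A reader looking for post-cessation events would have to know to search the general AE tables instead.

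**Working it through.** No sample size or error rate is involved, and the plan gives no figure to reproduce. SAP 4.5 says: "The study is not statistically powered, and all analyses are of descriptive nature". The check sets the definitions side by side and counts what the window can hold.

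1. **Window against target.** The target is onset after the last dose. The window ends at the last dose (SAP 3.2.2.2.5). The two do not overlap.

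2. **Follow-up time covered.** The Safety Follow-Up Visit is 30 ± 3 days after the last dose (SAP 3.2.2.1.4 and, for the Confirmatory Cohorts, 3.2.2.6), so post-cessation follow-up is 30 − 3 = 27 to 30 + 3 = 33 days. Days inside the window: 0 of 27 to 33. Down-titration lasts at most 7 days. Its share of taper plus follow-up is at most 7/(7 + 27) = 20.6% to 7/(7 + 33) = 17.5%, all of it before cessation.

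3. **Subjects covered.** At least 6 Exploratory subjects of at least 42 are planned (SAP 2.4): 6/42 = 14.3%. None can have an event in the window. The outputs are described as being for the Safety Set, which includes them. If the whole Safety Set were the denominator, a Confirmatory rate would shrink by 36/42 = 0.857 from this cause alone.

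4. **Is the narrowing declared or explained?** SAP 3.10 lists one change to protocol-defined analyses, the seizure-cause subgroups. The cohort restriction is not there. Version lag does not explain it: the amendment history shows the two-cohort sentence in Protocol 11.3.8 at Amendment 3, and SAP section 1 says the SAP is based on Amendment 6.

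5. **Where do the events go?** SAP 10.2 defines TEAEs with no upper time limit. SAP 10.2.1 tabulates them by period, including Safety Follow-Up and the entire study, by cohort including Exploratory, and lists all AEs. Post-cessation events therefore appear there, without being identified as withdrawal or rebound.

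6. **Subjects who stop early.** Protocol 5.1.2 lets the taper run in parallel with the Evaluation Period, whereas SAP 3.2.2.2.5 starts it only afterwards. An Exploratory infant given one dose is in the 48-hour Evaluation Period (SAP 3.2.2.1.2) and in Safety Follow-Up at the same time, with no stated precedence.

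7. **Washout, for illustration only.** Protocol 2.2 gives a half-life of about 9 h, alongside adult data. Five half-lives are 5 × 9 = 45 h. If the neonatal value were half or double that (an assumption), the figure would be 5 × 4.5 = 22.5 h to 5 × 18 = 90 h. Counted from the last dose, all of it falls after the window closes.

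**The case against.** The strongest reply is that nothing goes unreported. The Safety Follow-Up TEAE table is in effect a post-cessation table for Exploratory infants, the Confirmatory equivalent follows down-titration, and every AE is listed. This stands. A reader might infer from SAP 10.4.11 alone that post-cessation and Exploratory events are missed by the study; SAP 10.2.1 does not support that. The remaining fault is that the outputs bearing the variable's name cannot show it, and the general tables neither label withdrawal events nor anchor onset to the last dose.

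It can also be said that tapering is itself withdrawal, so the window is incomplete rather than wrong. That is fair, and taper-onset events should stay. SAP 10.4.11 does say that AEs relating to withdrawal will be used, but it gives no rule for selecting them and no output other than the onset-window ones.

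A reader might further infer that many Confirmatory infants stop with no taper, because Protocol 5.1.2 only recommends one. Other passages say that subjects proceed to it or should start it (Protocol 8.2.3 and 5.1.2, SAP 3.2.2.2.4), and no number can be derived.

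Finally, follow-up of about 30 days will collect unrelated events in infants with many anticipated background SAEs (Protocol 11.1.1.2.1). This is a reason to report time since last dose, not to close the window at the last dose.

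**Conclusion.** The point holds for the dedicated outputs in SAP 10.4.11. Followed as written, the two summaries and the listing contain no post-cessation AE (0 of 27 to 33 days) and no Exploratory subject (0 of at least 6). This conflicts with the SAP's own statement of the target and with Protocol 11.3.8.

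The consequence is limited. It is an other safety variable in a descriptive study, the events are reported elsewhere, and no primary or secondary result changes. The plan should still be corrected, because this is a stated rule that gives the wrong content rather than a missing detail.

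The conclusion rests on the SAP period definitions being applied literally. It does not depend on the half-life. The at least 6 Exploratory infants are the planned cohort, not the number at risk: subjects who continue BRV into the long-term study (SAP 3.2.4) have no cessation here.

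**What to change.** In SAP 10.4.11:

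- Set the onset window from the start of down-titration, or from the last BRV dose where there is none, through the Safety Follow-Up Visit.
- Show taper onset and post-last-dose onset separately, and give time since last dose in the listing so that late background events can be told apart.
- Include the Exploratory Cohort, as in Protocol 11.3.8.
- Use as denominator the Safety Set subjects who began down-titration or stopped BRV within the study, excluding those who roll over on BRV.
- State which period takes precedence when BRV stops before the Evaluation Period ends.

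The cost is SAP wording and a re-cut of one set of outputs from AE and dosing dates already collected. No visit, procedure or treatment rule changes.

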10.5 AED plasma level monitoring

Listing of AED plasma level monitoring will be provided for the SS.

10.6 Drug-Induced Liver Injury (DILI)

Where applicable, the following listings will be provided for the SS: family medical history for suspected DILI cases, hepatic event supplemental medical history, information on potential hepato-toxic medications injury, physical examination for DILI, symptoms of hepatitis and hypersensitivity, most recent study medication administration for DILI, local laboratory tests for DILI and vital signs for DILI.

^a Total cholesterol to be measured if this is part of the local lab's standard panel for neonates.

^b Urinalysis to be performed only if a urine sample was obtained for clinical purposes. A urine dipstick is acceptable.

^c TSH and T₄ to be recorded for the study only if measured for neonatal screening of congenital hypothyroidism prior to or during study participation.

12.2 Potentially clinically significant treatment-emergent criteria (PCST) for neonates (postnatal age up to 1 month)

Introduction

This document defines rules to be applied in the safety analyses of the UCB Pharma, Inc. clinical development programs in CNS Therapeutic Area. Rules for detecting possibly clinically significant treatment-emergent laboratory values, vital signs, and ECG parameters are considered. The purpose of this document is to bring consistency to reviewing laboratory data without over-riding the Investigator's clinical assessment of these parameters within the clinical context of the study subject.

POSSIBLY CLINICALLY SIGNIFICANT TREATMENT-EMERGENT (PCST) CRITERIA

These possibly clinically significant treatment-emergent (PCST) values are based on grade 2 toxicity if appropriate grading is available for age group, based on abnormal values or clinical experience based on discussion with [REDACTED] (see comments).

This document cannot be used to support any marketing authorization application and any extensions or variations thereof.
PUBLIC COPY

12.2.3 Chemistry (without Bilirubin)

Parameter	low	high	Comment
Calcium mg/dL (mmol/L)	<7d: <6.5 (<1.63)	<7d: ≥12.4 (≥3.1)	Grade 2 toxicity based on DAIDS criteria ⁴
	≥7d: <7.8 (<1.95)	≥7d: ≥11.5 (≥2.88)	
Potassium mEq/L (mmol/L)	<3.0	>6.0	Grade 2 toxicity based on DAIDS criteria ⁴
Sodium mEq/L (mmol/L)	<130	≥150	Grade 2 toxicity based on DAIDS criteria ⁴
Glucose mg/dl (mmol/L)	<50 (<2.22)	>160 (>13.89)	Grade 2 toxicity based on DAIDS criteria ⁴
AST/ALT/ALP	n/a	>2.5 ULN	Grade 2 toxicity based on DAIDS criteria ⁴

12.2.4 Chemistry (Bilirubin)

Bilirubin mg/dl			
Postnatal Age	GA<38	GA≥38	Comment
≤12 h	6	8	Considered PCST if bilirubin values reach cutoff for phototherapy recommendation, considering neonates with risk factors Based on AAP guideline 2004 ⁶
>12 h and ≤ 24 h	8	10	
>24 h and ≤ 48 h	11	13	
>48 h and ≤ 72 h	13	15	
>72 h and ≤ 96 h	14	17	
> 96h	15	18	

⁶ Management of Hyperbilirubinemia in the Newborn Infant 35 or More Weeks of Gestation, AAP, PEDIATRICS Vol. 114 No. 1 July 2004

12.3 PDILI

Laboratory value	
ALT or AST	Total bilirubin
$\geq 3\times \text{ULN}$ ^b	$\geq 2\times \text{ULN}$ ^{ab}
$\geq 3\times \text{ULN}$	NA
$\geq 5\times \text{ULN}$ (and $\geq 2\times$ baseline)	$< 2\times \text{ULN}$
$\geq 3\times \text{ULN}$ (and $\geq 2\times$ baseline) and $< 5\times \text{ULN}$	$< 2\times \text{ULN}$

^a If the subject also has $\geq 2\times \text{ULN}$ ALP, the possibility of an indication of biliary obstruction should be discussed with the Medical Monitor.

^b The criteria of Hy's Law are (ALT or AST $\geq 3\times \text{ULN}$) and total bilirubin $\geq 2\times \text{ULN}$.

This document cannot be used to support any marketing authorization application and any extensions or variations thereof.
PUBLIC COPY

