6.3.1 Potential drug-induced liver injury IMP discontinuation criteria

Subjects with potential drug-induced liver injury (PDILI) must be assessed to determine if the investigational medicinal product (IMP) must be discontinued. In addition, all concomitant medications that are not medically necessary should also be discontinued.

The PDILI criteria below require immediate and permanent discontinuation of IMP:

- Subject has direct (conjugated) bilirubin >2 mg/dL.
- Subject has AST, ALT or ALP values >3 x ULN, with the following exception:

For subjects with perinatal asphyxia, elevation of AST, ALT or ALP <5 x ULN is acceptable for continuation in the study, if initial and peak LFT elevation occurs within 5 days after birth, and if the time course of LFT elevation is compatible with hepatic injury due to perinatal asphyxia (ie, peak LFT elevation within few days after birth, and subsequent normalization until up to day 14 after birth).

In case AST, ALT or ALP elevation ≥ 5 x ULN occurs within 5 days after birth, study drug must be discontinued and LFTs retested within 24 hours. If AST, ALT and ALP are confirmed to be <5 x ULN, the subject may restart study drug after consultation with and approval by the Medical Monitor.

The determination of ULN will be based on the subject's GA and the site's normal range values for the respective GA.

- Subject requires or is expected to require phototherapy or exchange transfusion due to elevation of total bilirubin values.

Investigators should attempt to obtain information on subjects in the case of IMP discontinuation to complete the final evaluation. Subjects with PDILI should not be withdrawn from the study

until investigation and monitoring are complete. All results of these evaluations and observations, as well as the reason(s) for IMP discontinuation and subject withdrawal (if applicable), must be recorded in the source documents. The eCRF must document the primary reason for IMP discontinuation.

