11.1.1.3 Adverse events of special interest

An AE of special interest is any AE that a regulatory authority has mandated be reported on an expedited basis, regardless of the seriousness, expectedness, or relatedness of the AE to the administration of a UCB product/compound.

The following will be considered AEs of special interest for the study population:

- Autoimmune nephritis
- Nephritis
- Nephritis allergic
- Tubulointerstitial nephritis
- Tubulointerstitial nephritis and uveitis syndrome
- Potential drug-induced liver injury as indicated by:
 - Direct (conjugated) bilirubin >2 mg/dL
 - Condition requiring phototherapy or exchange transfusion due to elevation total of bilirubin values
 - AST, ALT or ALP values ≥ 3 x ULN according to the subject's GA and the site's normal values for that GA, with the following exception:

For subjects with perinatal asphyxia, if initial and peak LFT elevation occurs within 5 days after birth, and if the time course of the elevation of LFT is compatible with hepatic injury due to perinatal asphyxia (ie, peak LFT elevation within few days after birth, and subsequent normalization until up to day 14 after birth) only AST, ALT or ALP elevation ≥ 5 x ULN must be reported as an AE of special interest.

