2.4 Determination of sample size

At least 42 evaluable subjects will be enrolled in this study, with at least 6 subjects in the Exploratory Cohort and at least 36 subjects will be enrolled in 3 successive Confirmatory Cohorts, each consisting of 12 subjects. At least 2 subjects undergoing hypothermia treatment will be included in the Exploratory Cohort and each of the 3 Confirmatory Cohorts.

Subjects in the Exploratory Cohort might be replaced due to lack of data, as deemed necessary following the review of PK and safety data by the DMC.

No formal sample size calculation has been performed as a single treatment BRV arm is planned for descriptive summary results and for comparison with the 6 subjects from the Exploratory Cohort. The total number of at least 36 subjects in the Confirmatory Cohorts is expected to provide sufficient evidence of tolerability, safety, and efficacy, as well as good precision for the PK profile of BRV in neonates.

Confirmatory Cohort subjects who drop out or are withdrawn from study participation will not be replaced.

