10.3.2 Potential Drug Induced Liver Injury

A summary of the number and percentage of subjects who met PDILI criteria at any point in time will be summarized overall, and by cohort for all subjects. Results from local laboratory testing should be included, if applicable. Subjects who meet one or more of the criteria for potential drug-induced liver injury (PDILI) at any point in time will be listed. The listing will display all assessments for which at least one of the criteria for PDILI (see [Appendix Error! Reference source not found.](#)) was fulfilled for a given subject, and will display all results obtained at that time for the specified variables associated with PDILI. Potential Hy's law cases will be flagged.

All PDILI events require immediate action, testing, and monitoring. The measurements and additional information required for the assessment of PDILI events when there is a reasonable possibility that they may have been caused by the IMP are included but not limited to those listed in laboratory measurements.

Additional PDILI information will also be listed. If specific PDILI information collected separately is matching to the entries in the standard eCRF pages collected for all subjects, the specific PDILI information will be added to the corresponding listing for the standard eCRF information. For information collected on top (eg, family history of PDILI, lifestyle) a new listing will be generated.

Suspected hepatic events will be listed for the SS.

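### The SAP's PDILI table counts only ALT or AST ≥3×ULN, an undeclared departure from the protocol's criteria that both misses and adds babies

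*SAP*

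**What the plan says.** **SAP.** Section 10.3.2 promises "A summary of the number and percentage of subjects who met PDILI criteria at any point in time", overall and by cohort, plus a listing. Its pointer to the appendix holding the criteria is a broken cross-reference. Section 12.3 is the only PDILI appendix. It has four rows combining ALT or AST with total bilirubin, both in multiples of ULN:

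1. ALT or AST ≥3×ULN with total bilirubin ≥2×ULN
2. ALT or AST ≥3×ULN, bilirubin not applicable
3. ALT or AST ≥5×ULN and at least twice baseline, with total bilirubin <2×ULN
4. ALT or AST ≥3 and <5×ULN and at least twice baseline, with total bilirubin <2×ULN

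Footnote b, which opens "The criteria of Hy's Law are", labels the first row as Hy's Law. ALP appears only in footnote a, as a prompt to discuss biliary obstruction.

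**Protocol.** Section 6.3.1 gives three separate triggers:

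- "Subject has direct (conjugated) bilirubin >2 mg/dL"
- "Subject has AST, ALT or ALP values >3 x ULN, with the following exception", the exception being "For subjects with perinatal asphyxia, elevation of AST, ALT or ALP <5 x ULN is acceptable for continuation in the study", provided the timing and course fit hepatic injury from asphyxia
- "Subject requires or is expected to require phototherapy or exchange transfusion due to elevation of total bilirubin values"

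ULN is set by gestational age and site. Section 11.1.1.3 uses the same elements for adverse events of special interest (AESIs), and under the asphyxia exception "only AST, ALT or ALP elevation ≥ 5 x ULN must be reported as an AE of special interest". Table 11-3 also uses them. Exclusion criterion 7a lets asphyxia babies enter at <5×ULN under a similar exception.

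SAP 3.10, which lists changes to protocol-defined analyses, mentions only the seizure-cause subgroups.

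**The concern.** The protocol's PDILI criteria are neonatal: direct rather than total bilirubin, ALP alongside the transaminases, phototherapy or exchange transfusion as a trigger in its own right, and an allowance for liver injury from asphyxia. None of these decides who is flagged under SAP 12.3.

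Meeting a 6.3.1 criterion calls for stopping study drug, and 11.1.1.3 makes the same kind of event an AESI. A reader of the study report will expect the PDILI count to correspond to those discontinuations and AESIs. If the table runs on a different rule, it will not, and nothing in the SAP tells the reader why. Short-term safety is a secondary objective, and the study plans at least 42 babies, so even a few misclassified babies would change the table noticeably.

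**Working it through.** There is no planned figure to reproduce: the documents give no PDILI rate, and SAP 2.4 states that "No formal sample size calculation has been performed". The check compares the two rules.

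**Step 1: reduce SAP 12.3.** Let E be ALT or AST and B total bilirubin, both in ×ULN, and let E0 be baseline E.

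- Row 1: E ≥ 3 and B ≥ 2
- Row 2: E ≥ 3
- Row 3: E ≥ 5, E ≥ 2·E0, B < 2
- Row 4: 3 ≤ E < 5, E ≥ 2·E0, B < 2

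Rows 1, 3 and 4 each imply E ≥ 3, so the union of the four rows is row 2. Neither B nor E0 affects who is flagged.

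**Step 2: write the protocol rule.** Let A be ALP in ×ULN, D direct bilirubin in mg/dL, and P phototherapy or exchange transfusion. The rule is: D > 2, or P, or E ≥ t, or A ≥ t, with t = 3, or t = 5 under the asphyxia exception (its timing condition taken as met). The test values below avoid the cut-offs, so > versus ≥ makes no difference.

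**Step 3: compare single profiles.**

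| Profile | SAP 12.3 | Protocol |
|---|---|---|
| ALT 3.5×ULN, no asphyxia | flagged | flagged |
| ALT 6×ULN, asphyxia | flagged | flagged |
| Total bilirubin 2.5×ULN alone | not flagged | not flagged |
| ALP 4×ULN alone | not flagged | flagged |
| Direct bilirubin 2.5 mg/dL alone | not flagged | flagged |
| Phototherapy alone | not flagged | flagged |
| ALT 4×ULN, asphyxia exception | flagged | not flagged |

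**Step 4: confirm on a full grid.** E and A each take 1, 2.5, 3.5, 4.5 and 6; B takes 1 and 2.5; D takes 0.5 and 2.5; P and asphyxia are yes or no; E0 takes 1 and 2.5. That gives 5×5×2×2×2×2×2 = 800 cells.

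- SAP-positive: 3 of 5 levels of E, so 480. Of these, protocol-negative cells need the exception, E of 3.5 or 4.5, A below 5 (4 levels), D = 0.5 and no P: 2×4×2 (B)×2 (E0) = 32. Both positive: 480 − 32 = 448.
- SAP-negative: 800 − 480 = 320. Of these, protocol-negative cells need E of 1 or 2.5, D = 0.5, no P, and A at 2 levels without asphyxia or 4 with it: 2×(2+4)×2×2 = 48. Missed by the SAP: 320 − 48 = 272.

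The rules disagree in both directions: 272 cells missed, 32 added. Cell counts show direction only and say nothing about how common each profile is.

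**Step 5: entry values.** SAP 10.3.2 sets no time restriction. An asphyxia baby admitted under exclusion 7a at 3 to <5×ULN could therefore count as PDILI on its entry value.

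**The case against.** The strongest reply is that no safety information is lost. Direct-bilirubin, ALP and phototherapy cases are AESIs under protocol 11.1.1.3 and must be reported immediately. A PDILI event leading to discontinuation must also be reported as an SAE (11.2.1). SAP 10.2.1 tabulates serious TEAEs and TEAEs leading to permanent discontinuation. SAP 10.3.2 and 10.6 list suspected hepatic events and DILI details, and all chemistry results are listed. The PCST criteria include ALP >2.5×ULN (12.2.3) and bilirubin cut-offs tied to phototherapy recommendations (12.2.4). All analyses are descriptive.

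This stands as a limit on the consequence, and it rules out the reading that these cases vanish from the report. It does not repair the PDILI table. The PCST criteria feed a different summary with different cut-offs, and the TEAEs of interest come from a sponsor file that the SAP does not tie to the protocol's AESI list.

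Two further replies also narrow the point. First, the rules agree for babies without asphyxia at ALT or AST above 3×ULN and for asphyxia babies above 5×ULN, so it would be wrong to infer that the table flags the wrong babies in general. Second, a reader might infer from the total-bilirubin column that jaundiced babies will be over-flagged. They will not: no row flags on total bilirubin alone.

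It could also be argued that the broken reference leaves programmers free to use the protocol's definition. But 12.3 is the only PDILI definition in the SAP, and the SAP's change log records 10.3.2 and 12.3 as added in the same amendment.

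**Conclusion.** The point holds in limited form. Followed as written, SAP 12.3 gives a PDILI count that differs from the protocol's definition in both directions, and SAP 3.10 does not declare this. The table is inconsistent with the protocol rather than merely short of detail, so it should be corrected. The consequence is a summary that will not reconcile with PDILI discontinuations and AESIs.

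The number of babies affected cannot be derived. A reader might apply the 42% HIE share from protocol 2.1 and get 0.42 × 36 = 15.1 babies in the Confirmatory Cohorts, or 0.42 × 42 = 17.6 overall, and then assume that some fraction has enzymes at 3 to <5×ULN. The documents do not support that. The 42% comes from a population-based study, not this trial's case mix. The exception turns on perinatal asphyxia with a defined timing and course, not on HIE. No document gives the fraction in that enzyme range, or the frequency of isolated direct-bilirubin, ALP or phototherapy cases.

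The conclusion assumes that 12.3 is what 10.3.2 is meant to cite and, for the babies wrongly added, that the exception's timing condition is met.

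**What to change.** 1. **Reconcile the protocol first.** Section 6.3.1 uses >3×ULN and >2 mg/dL; 11.1.1.3 uses ≥3×ULN and >2 mg/dL; Table 11-3 uses ≥3×ULN and ≥2 mg/dL. Section 6.3.1 also includes expected need for phototherapy or exchange transfusion, while 11.1.1.3 and the Table 11-3 footnote refer only to actual need. The sponsor must settle these; no threshold is preferred here.
2. **Replace the table in SAP 12.3** with the reconciled definition: direct bilirubin, AST/ALT/ALP against gestational-age-specific ULN, phototherapy or exchange transfusion, and the asphyxia exception.
3. **Repair the reference in SAP 10.3.2** so that the count and listing use that table.
4. **Keep Hy's Law** as a supplementary flag, labelled as such.

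The cost is an appendix edit and programming. ALP and direct bilirubin are already mandatory measurements in both documents. Phototherapy and the asphyxia exception cannot be programmed from laboratory data alone: they must come from procedure, AESI and medical-history records, with clinical review of whether the enzyme time course fits the exception.
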